1.1 Short title

Hand Ice-Pack vs Thermoneutral Pack RCT

1.2 Trial registration

Not prospectively registered (laboratory, minimal-risk, non-therapeutic investigation).

1.3 Protocol version and date

Version 1.0; 2025-10-03.

1.4 Roles and responsibilities

Sponsor/Institution: Poznań University of Physical Education (Department of Physical Therapy and Sports Recovery).

Scientific lead: [[name]], PhD. Data management/statistics: [[name]], MSc. Thermal imaging lead: [[name]], MSc.

Corresponding author: [[name]], [[contact]].

2. Background and Rationale

Local cryotherapy with ice packs is widely used to alleviate pain and modulate cutaneous temperature and sensation. However, the short-term time-course of rewarming and contemporaneous changes in subjective thermal perception and somatosensory thresholds are not fully characterised in controlled, randomized settings. This study compares a 15-minute hand ice-pack application with a thermoneutral water-pack control, using infrared thermography (IRT) and a resistance thermometer (RT) alongside validated subjective scales and quantitative sensory testing (QST).

3. Objectives

Primary objective:

- To compare the effect of ice-pack vs thermoneutral pack on dorsal hand skin temperature (Tsk) during early rewarming after a 15-minute application.

Secondary objectives:

- To compare immediate post-cooling changes in mechanical detection threshold (MDT) and vibration detection threshold (VDT).
- To compare trajectories and peaks of subjective thermal sensation (TSS), thermal comfort (CS), and pain (VAS) during cooling and immediately post-cooling.
- To characterise agreement and systematic offset between ROI-averaged IRT and single-site RT across matched time points.

4. Trial Design

Randomized, parallel-group, two-arm laboratory experiment with a 1:1 allocation ratio (ice vs thermoneutral water). Single-centre. No blinding of participants; thermal image analysis performed offline by a rater not involved in data collection.

5. Study Setting

Single air-conditioned laboratory (Department of Physical Therapy and Sports Recovery, Poznań University of Physical Education). Ambient conditions monitored throughout (target $\sim 22.5 \pm 1.0$ °C, $55 \pm 7\%$ RH).

6. Participants

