8.2 Key secondary endpoints

- Dorsal hand Tsk at matched time points (I, IV–X) by IRT and RT; between-group differences and IRT–RT offsets.
- MDT change (post-cooling minus baseline; IV–I).
- VDT change (IV–I).
- Subjective scales: TSS (−4 very cold ... +4 very hot), CS (1 comfortable ... 5 extremely uncomfortable), VAS pain (0–100 mm). Outcomes include peak during cooling (II/III) and immediate post-cooling (IV).

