8.3 Safety/harms

Monitoring for intolerance to cold (excess pain, numbness), skin irritation, or adverse events (e.g., frostbite risk). None anticipated under protocol; record and report any events.

9. Time Schedule of Enrolment, Interventions, and Assessments

Acclimatisation: 15 minutes (supine, hand supported on insulating mat).

Measurements at the following time points:

- I – end of acclimatisation (baseline)
- II – 7th minute of cooling
- III – 15th minute of cooling
- IV – immediately after removing the pack
- V – 5th minute of rewarming
- VI – 10th minute of rewarming
- VII – 15th minute of rewarming
- VIII – 20th minute of rewarming
- IX – 25th minute of rewarming
- X – 30th minute of rewarming

Schedule (✓ = administered):

- IRT (ROI mean Tsk): I, IV–X (eight images total)
- RT (single-site Tsk): continuous at 1-min; aligned to I–X for analysis
- TSS, CS, VAS: I, II, III, IV
- QST (MDT, VDT): I and IV

10. Data Collection Methods

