12.3. Blinding

Participants and interventionists were not blinded. Thermal image analysis was performed offline by an assessor not involved in data collection. Raw-data preprocessing/curation ([name]) and statistical analyses ([name]) were conducted by team members who did not take part in the experimental procedures and were blinded to group allocation.

13. Statistical Analysis Plan (SAP)

- **Descriptives:** values as mean \pm SD; Table 1 additionally reports min–max where shown.
- **Normality:** Shapiro–Wilk test.
- **Between-group comparisons at prespecified time points:** Student’s t test (normal) or Mann–Whitney U test (non-normal).
- **Within-group pre–post comparisons:** paired Student’s t test (normal) or Wilcoxon signed-rank test (non-normal).
- **Repeated measures:** two-way repeated-measures ANOVA for Tsk (group \times stage; and IRT vs RT within groups), with Bonferroni-adjusted post hoc tests. Effect size: partial η^2 for RM-ANOVA.
- **Significance:** $\alpha = 0.05$; tests two-sided.
- **Analysis set / missing data:** all randomised participants analysed; no imputation (no losses).

14. Data Management and Sharing

De-identified individual participant data (IPD) and the de-identified summary datasets underlying all tables and figures are openly available in Zenodo (DOI: 10.5281/zenodo.17255092) under a CC BY 4.0 license, with no access restrictions or data-use agreement required. The Zenodo record also includes Supplementary File S1 (exact questionnaire wording/anchors) and the full Research Protocol and prespecified Statistical Analysis Plan. De-identified IPD comprise participant-level values for prespecified outcomes and baseline characteristics; direct identifiers, dates, free-text fields, and rare categories were removed or aggregated to minimise re-identification risk. The dataset will be preserved for at least 5 years; enquiries may be directed to the corresponding author.

15. Ethics

Approved by the Bioethics Committee of the Poznań University of Medical Sciences (Resolution No. 360/11). Conducted in accordance with the Declaration of Helsinki. Minimal risk expected.

16. Monitoring and Harms

Adverse events (e.g., excessive pain, skin irritation) monitored throughout; any event recorded with timing, severity, relatedness, and action taken. No interim analyses; trial duration per session ~60–75 minutes.

17. Amendments and Deviations

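### Comparing the trajectories of TSS, CS and VAS is a secondary objective, but no planned test asks whether the between-arm difference in these scales changes across stages

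*Combined protocol and SAP*

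**What the plan says.** - **Objective (section 3).** One secondary objective is "To compare trajectories and peaks of subjective thermal sensation (TSS), thermal comfort (CS), and pain (VAS"), covering the cooling period and the moment just after it. It names course and peak as two separate targets.
- **Schedule (section 9).** The three scales are collected at four stages: "TSS, CS, VAS: I, II, III, IV". These are baseline, minute 7 of cooling, minute 15 of cooling, and pack removal.
- **Endpoints (section 8.2).** For the scales, "Outcomes include peak during cooling (II/III) and immediate post-cooling (IV"). No slope, area under the curve or change score is listed for them, although MDT and VDT are defined as the change IV–I.
- **Analysis (section 13).** The longitudinal method is a "two-way repeated-measures ANOVA for Tsk", with a group × stage term. Bonferroni adjustment is attached only to its post hoc tests. The other tests name no outcome. Between groups at prespecified time points, the plan uses "Student’s t test (normal) or Mann–Whitney U test (non-normal"). Within groups, pre to post, it uses "paired Student’s t test (normal) or Wilcoxon signed-rank test (non-normal"). Alpha is 0.05, two-sided.

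**The concern.** A trajectory comparison asks how the ice–control difference behaves over time: whether it grows from minute 7 to minute 15, and whether it persists or shrinks when the pack comes off. The plan applies such a test to Tsk, so the authors had the tool in hand, but it does not extend the test to the ratings.

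Without it, a statement that the course of pain, comfort or thermal sensation differed between arms would have no planned inference behind it. A difference that is significant at one stage and not at the next does not show that the difference changed. Neither does a change that is significant in one arm and not in the other. What is at stake is whether the report can answer this part of its own objective.

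**Working it through.** **The plan's own figures.** Section 11 states 26 per group for a two-sided t-test at d = 0.80, alpha 0.05 and power 0.80, and power of about 0.68 with 20 and 19. The noncentral t distribution gives 26 per group (power 0.807) and 0.682, so both figures reproduce. They concern one two-sample comparison and say nothing about power for a group × stage effect.

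**Which question each planned test answers.** Let D(s) be the true ice-minus-control difference on one scale at stage s.

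1. *Between-group test at one stage.* Null: D(s) = 0. This concerns level at that stage.
2. *Within-group pre–post test.* Null: no change in one arm. D does not appear.
3. *Group × stage test over II, III and IV.* Null: D(II) = D(III) = D(IV). This concerns course, and section 13 plans it for Tsk only.

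Tests 1 and 2 can be repeated at every stage without ever testing null 3. If D is the same non-zero value at II, III and IV, stage-wise tests may still be significant at some stages and not at others by chance.

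**What stage I adds.** Section 12.2 conceals allocation until baseline assessments are finished, so D(I) is zero in expectation. A true non-zero D(s) at a later stage therefore already means that the arms moved apart from baseline. The planned stage-wise tests can show this. They cannot show how the separation evolves after it appears.

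**Multiplicity, as illustration only.** The plan does not state how many tests the scales will receive. For k independent tests at 0.05, the familywise error is 1 − 0.95^k. Under any dependence it lies between 0.05 (tests fully dependent) and k × 0.05.

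| Assumed set | k | If independent | Range under dependence |
|---|---|---|---|
| 3 scales × (II, III, IV) | 9 | 1 − 0.95^9 = 0.37 | 0.05 to 0.45 |
| 3 scales × (peak, IV) | 6 | 1 − 0.95^6 = 0.26 | 0.05 to 0.30 |

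The second row counts the peak over II and III as one value per scale. Repeated ratings in the same people are correlated, so the independence column is a reference value and not an estimate. The table describes the cost of many uncorrected tests; it does not measure the missing interaction test.

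**The case against.** The strongest reply is that the plan already compares the arms on these scales. The between-group tests are not limited to any outcome, the arms are randomised, and the section 8.2 outcomes (peak during cooling and value at IV) are quantities that those tests handle. Only three post-baseline ratings exist, and III and IV fall at the end of cooling and at pack removal, so stage-wise comparisons describe much of the course. The objective is secondary, and section 11 calls the findings exploratory.

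Most of this stands, and it limits the point. A reader might infer that the objective has no valid between-arm test at all, or can be judged only by eye. The documents do not support that: levels and peaks are covered. A reader might also infer that the authors mean to compare arms by setting within-arm p-values side by side, and might size the problem by how often two such tests disagree. Section 13 does not say that paired tests will be used in that way, so no such figure is used here. Nor does the plan state a nine-test set, so 37% is not the plan's error rate.

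The reply leaves one thing unanswered. Section 3 lists trajectories in addition to peaks, and no planned test addresses whether D changes across stages. An exploratory label lowers the weight of the gap but does not supply the analysis.

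**Conclusion.** The objective and the analysis do not match for the trajectory part of one secondary objective. This conclusion needs no numerical assumption: it rests on section 3 naming trajectories, section 13 confining the group × stage analysis to Tsk, and no other section supplying an equivalent. Comparisons of level are valid, and the primary endpoint is unaffected. The weight is moderate: the omission is worth correcting because the data exist and the cost is small, but it does not undermine the trial. The 37% and 26% figures assume independent tests at 0.05 and test sets that the plan does not state.

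**What to change.** Add to section 13, for each scale, one group × stage analysis over II, III and IV that accounts for the stage-I value:

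- **TSS and CS:** a rank-based ANOVA-type test, for example on change from stage I. With 20 and 19 participants this is safer than a cumulative-logit mixed model, which may be unstable if control ratings hardly vary.
- **VAS:** a linear mixed model with the stage-I value as covariate and small-sample or robust standard errors.
- **Reporting:** give the overall group effect and the group × stage effect. Two effects on three scales make six tests, so state a multiplicity adjustment across the scales or label the results explicitly as exploratory. Treat within-group tests as descriptive.
- **Status:** section 11 reports enrolment as complete and section 14 says the data are already public. Record the addition as a dated amendment under section 17 and label it post hoc.

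If the sponsor prefers not to add analyses, restrict the section 3 objective to the peak and stage-IV comparisons of section 8.2, and draw no between-arm conclusion about trajectories.

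The cost is three extra models on data already collected, plus SAP wording. Power for the interaction will be low if control ratings hardly vary, so a non-significant group × stage result should not be read as showing equal trajectories.

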6.1 Eligibility criteria

Inclusion: healthy males, university students, good general health, no history of neck/upper-quadrant pain.

Exclusion: diabetes; thyroid or other endocrine disorders; significant spinal pain; generalised neurological/rheumatological disorders; regular analgesic or psychotropic medication use.

6.2 Recruitment

Oral announcements among university student population.

6.3 Informed consent

Written informed consent obtained prior to any procedures.

7. Interventions

7.1 Cooling intervention (experimental)

Commercial plastic ice bag (\varnothing 22.86 cm; capacity ~946 ml). Filled with 400 g of pre-portioned cylindrical ice cubes (20 g each). Applied to the dorsal hand, ~1 cm proximal to the wrist joint line, covering fingers. Duration: 15 minutes.

7.2 Thermoneutral control

Same bag, filled with water at thermoneutral temperature (equal to current limb temperature \pm 0.5 °C), mass-matched to 400 g. Same placement and duration.

7.3 Concomitant care

Participants refrained from topical agents on hands 24 h prior; abstained from smoking, alcohol, coffee, intense exercise on test day. Hands washed/degreased \geq 1 h before data collection.

8. Outcomes and Endpoints

8.1 Primary endpoint

- Minimum dorsal hand Tsk during the 30-minute rewarming window (IV–X) measured by IRT (ROI mean); between-group difference (ice vs control).

8.2 Key secondary endpoints

- Dorsal hand Tsk at matched time points (I, IV–X) by IRT and RT; between-group differences and IRT–RT offsets.
- MDT change (post-cooling minus baseline; IV–I).
- VDT change (IV–I).
- Subjective scales: TSS (−4 very cold ... +4 very hot), CS (1 comfortable ... 5 extremely uncomfortable), VAS pain (0–100 mm). Outcomes include peak during cooling (II/III) and immediate post-cooling (IV).

8.3 Safety/harms

Monitoring for intolerance to cold (excess pain, numbness), skin irritation, or adverse events (e.g., frostbite risk). None anticipated under protocol; record and report any events.

9. Time Schedule of Enrolment, Interventions, and Assessments

Acclimatisation: 15 minutes (supine, hand supported on insulating mat).

Measurements at the following time points:

- I – end of acclimatisation (baseline)
- II – 7th minute of cooling
- III – 15th minute of cooling
- IV – immediately after removing the pack
- V – 5th minute of rewarming
- VI – 10th minute of rewarming
- VII – 15th minute of rewarming
- VIII – 20th minute of rewarming
- IX – 25th minute of rewarming
- X – 30th minute of rewarming

Schedule (✓ = administered):

- IRT (ROI mean Tsk): I, IV–X (eight images total)
- RT (single-site Tsk): continuous at 1-min; aligned to I–X for analysis
- TSS, CS, VAS: I, II, III, IV
- QST (MDT, VDT): I and IV

10. Data Collection Methods

10.1 Infrared thermography (IRT)

FLIR SC640 (NETD < 30 mK, 640×480, ±2% accuracy). Perpendicular camera mounting at ~90 cm. Emissivity set to 0.98; ambient control per guidance. ROI template on dorsal hand up to the wrist line. Software: Thermacam Researcher Pro 2.10. Images analysed offline by trained rater; 10% re-analysed for intra-rater consistency.

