10.2 Resistance thermometer (RT)

Contact sensor (~15 mm²) affixed between 3rd–4th metacarpals, mid-distance between wrist and MCP joints, secured with medical tape. 1-min sampling from acclimatisation start to end of rewarming. Two-point check vs reference thermometer before each session.

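### As written, the thermography region of interest contains the taped contact sensor at all eight image times, and no exclusion of sensor or tape pixels is stated

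*Combined protocol and SAP*

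**What the plan says.** - **Region.** Section 10.1 gives one rule for the IRT region of interest: "ROI template on dorsal hand up to the wrist line". It sets a single emissivity of 0.98, has a trained rater analyse the images offline, and has 10% re-analysed for intra-rater consistency. It mentions no exclusions.
- **Sensor site.** Section 10.2 places a contact sensor of about 15 mm² "between 3rd–4th metacarpals, mid-distance between wrist and MCP joints, secured with medical tape". That sentence does not say dorsal, but section 8.2 does, for both methods: "Dorsal hand Tsk at matched time points (I, IV–X) by IRT and RT; between-group differences and IRT–RT offsets".
- **Wear time.** Section 10.2 specifies "1-min sampling from acclimatisation start to end of rewarming".
- **Image times.** The schedule in section 9 lists "IRT (ROI mean Tsk): I, IV–X (eight images total" for IRT, and "RT (single-site Tsk): continuous at 1-min; aligned to I–X for analysis" for the sensor.
- **Use of the region mean.** It is the primary endpoint in section 8.1: "Minimum dorsal hand Tsk during the 30-minute rewarming window (IV–X) measured by IRT (ROI mean". It is also the IRT side of the agreement objective in section 3 and of the IRT-versus-RT repeated-measures ANOVA in section 13.

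**The concern.** Where sensor and tape cover the hand, the camera sees their outer surface and not skin. If that surface reads differently from the skin around it, the region mean carries a systematic error, which averaging over participants does not remove. The 10% re-read would not reveal it either, since the same unmasked template gives the same answer twice.

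The primary comparison is an ice-versus-control contrast, where a small shift may not matter. The IRT–RT offset is more exposed. It may itself be small, and part of the IRT value would be read from the surface of the device it is being compared with. If the error depends on skin temperature, it can differ by arm and by stage, which are the contrasts that section 13 analyses.

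**Working it through.** **Plan's own figures.** The plan gives no figure for this point. Its computed figures are in section 11 and reproduce with the noncentral t: power is 0.791 at 25 per group and 0.807 at 26 per group, hence 26; power is 0.682 at 20 and 19 (stated 0.68). This point does not challenge them.

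**Step 1: place.** The region is the dorsal hand up to the wrist line (10.1). The sensor is midway between wrist and MCP joints, between the third and fourth metacarpals (10.2), measuring dorsal skin (8.2). The site is well inside the region, not at its edge.

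**Step 2: time.** The sensor records from the start of acclimatisation to the end of rewarming. Images are taken at I and IV–X, so 8 of 8 image times fall within wear time.

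**Step 3: exclusions.** No section describes a mask, removal of the sensor for imaging, or use of the other hand.

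**Step 4: size, simple form.** Shift = covered share × (covered reading − skin). Assumed share 3–10% and assumed difference 1–3 °C:
- low: 0.03 × 1 = 0.03 °C
- high: 0.10 × 3 = 0.30 °C

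**Step 5: size and direction under a simple model.** Let f be the covered share and k the fraction by which the covered surface reads from skin towards ambient. Then

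region mean = Tskin + f·k·(Tambient − Tskin).

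Ambient is 22.5 °C (section 5 target). Assumed: region 80–180 cm², k 0.1–0.5, skin 10–32 °C.

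| Covered area | f | Shift, skin 10 °C | Shift, skin 32 °C |
|---|---|---|---|
| Sensor only, 0.15 cm² | 0.15/180 to 0.15/80 = 0.08–0.19% | at most +0.012 °C | at most 0.009 °C downwards |
| Assumed tape, 2–12 cm² | 2/180 to 12/80 = 1.1–15% | +0.01 to +0.94 °C | −0.01 to −0.71 °C |

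The extreme is 0.15 × 0.5 × 12.5 = 0.94 °C. It needs the largest tape, the smallest region, the largest k and the coldest skin together.

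**Step 6: primary endpoint.** The model rearranges to (1 − f·k)·Tskin + f·k·Tambient. With the same f, k and ambient temperature in both arms and at all times, the minimum falls at the same time point and the between-group difference is multiplied by (1 − f·k). With tape, f·k runs from 0.0111 × 0.1 = 0.1% to 0.15 × 0.5 = 7.5%. The difference shrinks by that much; it is not created.

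**Step 7: offset.** The shift changes sign where skin equals ambient. In a middle case (6 cm² on 120 cm², f = 0.05, k = 0.3) it is 0.05 × 0.3 × 12.5 = +0.19 °C at 10 °C and 0.05 × 0.3 × (−9.5) = −0.14 °C at 32 °C. The offset would then move by 0.05 × 0.3 × 22 = 0.33 °C between a cold and a warm hand, with no change in true agreement.

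**The case against.** **The overlap is inferred.** No sentence states it. The region rule names a surface and a proximal limit, not a full outline, and a trained rater may have left out a visible sensor. This stands. A reader might infer that the trial's region means are contaminated; the documents show only that the written rule includes the site and states no exclusion.

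**The physics is assumed.** Tape size, tape emissivity, lead route and region area are not given. No emissivity mismatch is shown, and different rewarming under tape is plausible but unquantified. The one documented area gives about 0.01 °C or less; everything larger comes from an assumed tape patch. This stands too, and it is why only ranges can be offered.

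**Other sources of error may be larger.** Section 10.1 states camera accuracy of ±2%. If that means percent of reading (an assumption), it is ±0.6 °C at 30 °C. A region mean and a single-site reading also differ by design. Both points are fair, but neither is a reason to leave in a removable component that may vary with arm and stage.

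**Arm-dependent error might suggest bias in favour of ice.** A reader might infer this. The documents do not support it: if covered pixels read towards ambient, the cooling effect is attenuated.

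**Changing the region now is post hoc.** Section 11 reports enrolment and follow-up as complete, and a new region alters the primary endpoint values. Section 12.3 states blinding for the curation and statistics staff, but describes the image assessor only as uninvolved in data collection. This stands, and the fix needs safeguards for it.

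**Conclusion.** The point holds for the plan as written: the stated region covers the sensor site at all eight image times with no exclusion, so following it literally averages sensor and tape pixels into the mean. Whether that happened in practice is not known.

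Its importance is low for the primary endpoint. The plausible effect is a slight attenuation of the ice-versus-control difference, provided that covered pixels read towards ambient to a similar degree in both arms. It matters more for the IRT–RT offset, where a shift of 0.03–0.30 °C (3–10% cover, 1–3 °C difference, both assumed) could be material if the offset is small. The near-1 °C extreme in the working shows how far the assumptions can be pushed and is not an estimate. This is a worthwhile, inexpensive refinement, not a threat to the main comparison.

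**What to change.** 1. In section 10.1, define the region to exclude sensor, tape and lead plus a small fixed margin, identically in every image and both arms. State the tape size.
2. If the existing region means were already masked, saying so closes the point.
3. If they were not, have the existing rater re-measure the stored images, without group labels where possible. Report masked and unmasked results side by side for the primary endpoint and the offset, and base the interpretation of the offset on the masked values.
4. Record the change with rationale, date and potential impact, as section 17 requires.

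**Cost.** Rater time for up to 39 × 8 = 312 images, if all were retained (offline analysis implies storage, but retention is not stated); a slightly smaller region; and a documented post-hoc change. No new participant procedure is needed. Masking does not remove the by-design difference between a region mean and a single site, so the offset should still be read with that in mind.
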